### 7.4.1 Study Therapy

Extent of exposure to study therapy is summarized for blinded therapy (ETV active or PBO), open-label ETV, active ETV (blinded active ETV or open-label ETV), and all therapy (blinded therapy or open-label ETV) by treatment regimen as follows:

- Time on therapy (weeks):  $(\text{last dose date of drug} - \text{first dose date of drug} + 1)/7$ .
- Cumulative dose: total amount (mg) of drug summed across dosing records.
- Average daily dose: cumulative dose divided by time on therapy.

Extent of exposure to study therapy is also summarized analogously for the following: Primary Cohort; All ETV Safety Cohort; by age randomization strata for each treatment regimen.

Time on study therapy is also described by a Kaplan-Meier plot and life table. Discontinuations from study therapy are considered events in this analysis, and are identified by subjects with non-missing last dose date of study therapy. For subjects who have not discontinued, time on study therapy is censored at the maximum of the last dose date of study drug (ETV blinded active or PBO, ETV open-label).

Time in long-term follow up is summarized by treatment regimen for long-term follow-up subjects in the Post-Year 1 Safety Cohort. Time in long-term follow-up (weeks) is defined as (last contact date - last dose date of study therapy)/7.

Time in off-treatment follow up is summarized by treatment regimen for off-treatment follow-up subjects in the Post-Year 1 Safety Cohort. Time in off-treatment follow-up (weeks) is defined as (minimum(last contact date, start date of alternative anti-HBV therapy - 1) - last dose date of study therapy)/7.

Dose interruptions of study therapy more than 3 days are summarized by treatment regimen. Reasons for interruption are also identified.

See [Section 8.9](#) for additional conventions.

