## **7.6 Safety**

The investigators determine the intensity of AEs and the relationship of AEs to study therapy. The investigators' terms are coded and grouped by system organ class using the latest version of the Medical Dictionary for Regulatory Activities (MedDRA) in production at BMS.

In order to account for AEs with multiple occurrences in the same subject, AE records are collapsed for each subject and preferred term when records have the same onset date, or when records are contiguous or overlapping (see [Section 8.10](#)). All AE presentations are based on collapsed records.

AEs are presented by system organ class and preferred term, both in descending order of incidence on ETV, unless specified otherwise.

AE presentations include both non-serious and SAEs as defined in the protocol, unless specified otherwise. If a subject had an AE with different intensities during the study period, then only the greatest intensity is reported.

On-treatment safety is assessed for the following 3 cohorts (see [Sections 6.1](#) and [6.3](#)):

- Through Week 48 on blinded therapy for treated subjects
  - ETV and PBO are assessed on treatment up to the Week 48 cut, ie, the earlier of (a) 54 weeks, the upper bound of the Week 48 visit window (see [Section 8.4](#)), and (b) the first dose of open-label ETV.
- After Week 48 on blinded therapy or on open-label ETV through Week 96 for the Year 2 Safety Cohort

- ETV, PBO BL and PBO OL are assessed on treatment after the Week 48 cut and up to 102 weeks, the upper bound of the Week 96 visit window (see [Section 8.4](#)).
- On ETV treatment for All ETV Safety Cohort

Note that AEs with onset on the first day of study therapy are considered on treatment, AEs with onset on the first day of ETV are considered on ETV treatment and AEs with onset on the first day of open-label ETV are considered on open-label ETV.

Follow-up safety is assessed for the following 3 cohorts (see [Sections 6.1](#) and [6.3](#)):

- During off-treatment follow-up for off-treatment follow-up subjects in the Post-Year 1 Safety Cohort
- During long-term follow-up for long-term follow-up subjects in the Post-Year 1 Safety Cohort.
- During alternative ETV follow-up for alternative ETV follow-up subjects in the Post-Year 1 Safety Cohort (select endpoints only).

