## 8.9 Derived Dates

Derived dates that are used commonly in analyses are defined as follows. Derivations of dose dates exclude rescue open-label ETV.

- First dose date of study therapy is the earliest start date of drug (ie, blinded therapy [ETV active or PBO] or open-label ETV) identified from valid dosing records, ie, non-missing start date and number of units per day > 0, from blinded therapy study medication CRFs. This date is used to identify treated subjects and to distinguish measurements across study periods. Note that this is also first dose date of blinded study therapy.

- Dose end date of study therapy is the latest start or end dates of drug (ie, blinded therapy [ETV active or PBO] or open-label ETV) identified from valid dosing records, ie, non-missing start or end date and number of units per day > 0 or total dose > 0. This date is used to assess time on study therapy.
- Last dose date of study therapy is the dose end date of study therapy derived only for subjects with an end of treatment subject status CRF indicating whether the subject completed the treatment period. This date is used to exclude data in antiviral activity and safety analyses, and to distinguish measurements across study periods.
- Dose end date of blinded therapy is the latest start or end date of blinded therapy (ETV active or PBO) identified from valid dosing records, ie, non-missing start or end date and number of units per day > 0, from blinded therapy study medication CRFs. This date is used to assess time on blinded study therapy.
- First dose date of open-label ETV is the earliest start date of open-label ETV identified from valid dosing records, ie, non-missing start date and total dose > 0, from open-label study medication CRFs. This date is used to distinguish measurements across blinded vs open-label treatment, and to assess time on open-label therapy.
- Dose end date of open-label ETV is the latest start or end date of open-label ETV identified from valid dosing records, ie, non-missing start or end date and total dose > 0, from open-label study medication CRFs. This date is used to assess time on open-label therapy.
- First dose date of active ETV is the first dose date of study therapy for ETV-randomized subjects, and the first dose date of open-label ETV for PBO-randomized subjects. This date is used to identify all ETV-treated subjects and to distinguish measurements across study periods.

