- Dose end date of active ETV is the dose end date of study therapy for ETV-randomized subjects and the dose end date of open-label ETV for PBO-randomized subjects. This date is used to assess time on active ETV.
- Last dose date of active ETV is the dose end date of active ETV derived only when the last dose date of study therapy is not missing.
- Start date of rescue open-label ETV is the earliest start date of rescue open-label ETV identified from valid dosing records, ie, non-missing start date and total dose > 0, from rescue open-label ETV study medication CRFs.
- Start date of alternative ETV therapy is the earliest start date of (1) rescue open-label ETV, or (2) concomitant ETV taken on treatment or during long-term follow-up.
- Start date of alternative anti-HBV therapy is the earliest start date of (1) rescue open-label ETV, or (2) concomitant anti-HBV medication taken on treatment or during long-term follow-up.
- Last contact date is the death date, if it exists, or the latest of the following dates: randomization; first or last dose of study therapy; adverse event onset or resolution; hepatitis B related diagnosis; laboratory test (safety, pregnancy, serology and virology); liver biopsy; physical measurement; physical exam; neurologic exam; vital sign; non-study medication start or stop; last contact from end of treatment or end of study subject status; Tanner staging.

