## 8.10 Collapsed AEs and Exposure-Adjusted Incidence Rates

In order to account for AEs with multiple occurrences in the same subject, AE records are collapsed for each subject and preferred term when:

- Records have the same onset date.
- The onset date of an event record is either the same day or 1 day later than the resolution date of a preceding event record (contiguous events).
- The onset date of an event record is after the onset date and prior to or on the resolution date of a preceding event record (overlapping events).

The collapsed record contains the earliest onset date (and time, if collected); latest resolution date (and time, if collected); highest intensity in the following order (highest to lowest: very severe, severe, moderate, or mild); AE type of SAE, if ever reported as a SAE, AE otherwise; latest causality, as determined by the last modification time stamp (highest causality in the following order [highest to lowest: related, not related], if records contain the same last modification time stamp with different causalities); treatment required of yes, if ever required; highest action taken in the following order (highest to lowest: drug discontinued, drug interrupted, dose reduced, dose increased, none); latest reported term, as determined by the last modification timestamp.

Incidence rates per 100 person-years of exposure (IR/100 P-Y) are defined as event count \* 100 / person-years of exposure (see [Section 7.6.5](#)). Exposure is defined as time on study therapy (see [Section 7.4.1](#)), plus 5 days for subjects who discontinued study therapy to account for on-treatment safety reporting.

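### SAP 8.10 divides events counted in limited windows by total time on study therapy, so the Week 48 and Year 2 exposure-adjusted rates, and the placebo switchers' part of the All ETV rates, are too low if it is followed as written

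*SAP*

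**What the plan says.** **Events.** SAP 7.6.2 (SAEs) and 7.6.5 (AEs and non-serious AEs with incidence of at least 5%) present event counts and exposure-adjusted rates for three on-treatment cohorts. SAP 7.6 limits the events in each:

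- Through Week 48: "ETV and PBO are assessed on treatment up to the Week 48 cut", which is the earlier of 54 weeks and the first open-label ETV dose.
- Year 2: "ETV, PBO BL and PBO OL are assessed on treatment after the Week 48 cut and up to 102 weeks".
- All ETV: events on ETV treatment. For placebo-randomised subjects this starts at open-label ETV.

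**Denominator.** SAP 8.10 defines the rate as events × 100 / person-years and continues: "Exposure is defined as time on study therapy", with 5 days added for subjects who discontinued. It refers back to SAP 7.4.1 and sets no limit by window or cohort.

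**Meaning of the term.** In SAP 8.9, "Dose end date of study therapy is the latest start or end dates of drug", where drug covers both blinded therapy and open-label ETV, and that date is the one used for time on study therapy. The time-on-therapy plot in SAP 7.4.1 uses the same term and censors at the later of the blinded and open-label dose dates. SAP 8.9 keeps other dates for narrower measures. Of the blinded dose end date it says "This date is used to assess time on blinded study therapy", and of the active-ETV dose end date "This date is used to assess time on active ETV". SAP 8.10 uses neither. SAP 7.4.1 also tabulates several exposure types: "Extent of exposure to study therapy is summarized for blinded therapy (ETV active or PBO), open-label ETV, active ETV", and all therapy.

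**The concern.** A rate is interpretable only if events and person-time cover the same interval. Here the events stop at a window bound while the person-time runs on to the last dose. As written:

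- the Week 48 rates carry later open-label time;
- the Year 2 rates carry Year 1 time as well as time beyond 102 weeks;
- placebo switchers in the All ETV table carry their blinded placebo time.

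The surplus differs by arm, because placebo subjects who switch have a longer planned course (to about Week 144, at most Week 192) than ETV subjects (to about Week 96, at most Week 144). The Week 48 table is the only full randomised comparison of ETV with placebo; the Year 2 tables show in addition a small group that stayed on blinded placebo. A distortion that differs by arm therefore matters most in the Week 48 table. Long-term paediatric safety is a stated secondary objective, and these are the rates meant to adjust for unequal exposure.

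**Working it through.** The plan states no exposure-adjusted rate, so there is no figure to reproduce.

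**Formula.** With a constant event rate, reported rate = true rate × (person-time inside the window / person-time in the denominator). Define F = denominator time / window time, the factor by which the rate is too low. With equal true rates, the false ETV/placebo ratio is F(placebo) / F(ETV).

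**Single subjects who complete therapy.** Open-label ETV starts at Week 52 and 5 days (0.7 week) are added at the end.

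| Path | Denominator (weeks) | Through Week 48 | Year 2 | All ETV |
|---|---|---|---|---|
| ETV, non-seroconverter, stops Week 96 | 96.7 | 96.7/52 = 1.86 | 96.7/44.7 = 2.16 | 1.00 |
| Placebo, switched, stops Week 144 | 144.7 | 144.7/52 = 2.78 | 144.7/50 = 2.89 | 144.7/92.7 = 1.56 |

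**Cohort level, by simulation (200,000 subjects per arm per scenario).**

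Inputs from the plan (SAP 5): 10% dropout per year; 10% placebo HBeAg seroconversion at Week 48; 2:1 allocation; the first 123 subjects accrued evenly over 2 years (104 weeks).

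Assumptions not in the plan:

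- accrual continues at the same pace to 180 subjects, 104 × 180/123 = 152 weeks;
- ETV seroconversion is 20–30% at Week 48 and 0–20% at Week 96;
- switchers' seroconversion is 0–20% at Week 96 and 0–10% at Week 144;
- non-seroconverters stop at Week 96–100 (ETV) or Week 144–148 (placebo);
- nobody seroreverts.

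Data cuts are at calendar week 152 for the primary analysis (104 + 48), 200 when all have reached Week 48, 248 when all have reached Week 96, and 344 at the end of therapy. All subjects treated by the cut are counted. Ranges are minimum to maximum over the scenarios.

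| Table, rule as written | F, ETV | F, placebo | False ratio |
|---|---|---|---|
| Through Week 48, primary analysis | 1.47–1.52 | 1.65 | 1.08–1.12 |
| Through Week 48, second analysis | 1.63–1.73 | 2.00–2.03 | 1.16–1.25 |
| Year 2 (second and Week 96 reports) | 2.2–2.5 | 2.7–2.8 (switched to open label) | not applicable |
| All ETV | 1.0 | 1.6–2.1 (switchers) | pooled F 1.16–1.20 |

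In the Year 2 tables, subjects still on blinded placebo have F of about 2.3–2.5.

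**Sensitivity to accrual.** If subjects 124–180 take 26 to 104 weeks to accrue, the false Week 48 ratio is 1.08–1.13 (primary) and 1.12–1.36 (second).

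**If an analyst chose another exposure type from SAP 7.4.1:**

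- Week 48 with blinded time. Primary: F is 1.09–1.14 (ETV) and 1.05 (placebo), ratio 0.92–0.96. Second analysis: 1.13–1.19 and 1.07, ratio 0.90–0.95. The error shrinks but reverses, because Week 48 seroconverters, assumed more frequent on ETV, stay blinded to Week 96.
- All ETV with active-ETV time: the error disappears.
- Year 2 with active-ETV time: F stays at 2.2–2.5 (ETV) and is 1.5–1.7 (switched placebo). With open-label time it is 0.71–0.93 for ETV, so the rate is too high, and 1.5–1.7 for switched placebo. No listed type fits.

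**The case against.** The strongest counter-argument is SAP 7.1, which says that in the Week 48 analysis all endpoints are cut off at Week 48 unless otherwise specified. If an exposure-adjusted rate is such an endpoint, and its person-time is cut with its events, the Week 48 error largely disappears in that analysis. That reading is possible, but the rule does not mention exposure, while SAP 8.10 does specify exposure and does not truncate it. The rule also cannot reach the Year 2 or All ETV windows.

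A second argument is that a programmer would pick the matching exposure type from SAP 7.4.1, which already summarises exposure for the All ETV Safety Cohort. This stands for the All ETV table, where the fault is closer to an ambiguous cross-reference. It stands only in part for Week 48 and not at all for Year 2.

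Third, nothing is decided on these rates. No test uses them, they are printed beside event counts, and exposure is tabulated separately. All of that stands and limits the consequence.

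Four stronger readings are tempting but not supported:

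- *Every exposure-adjusted rate is too low.* For ETV-randomised subjects in the All ETV table, time on study therapy equals time on ETV and F is 1.0.
- *Week 48 is the only ETV versus placebo display.* SAP 6.3 and 7.6 also show a blinded-placebo group in Year 2.
- *The ETV/placebo distortion reaches 1.4 to 1.5.* That needs follow-up over the whole therapy course (1.39–1.49 in a simplified calculation), but SAP 9 omits the Week 48 safety tables from the reports after the second analysis.
- *The plan is certain to show a false excess on ETV.* The direction depends on which exposure measure is programmed.

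**Conclusion.** The point holds in limited form. Read literally, SAP 8.10 mismatches events and person-time. The Week 48 and Year 2 AE and SAE rates are too low, and the All ETV rates are too low through the placebo switchers only. The size is about 1.5-fold (ETV) and 1.65-fold (placebo) for Week 48 at the primary analysis, with a false ratio of about 1.1, rising to about 1.2 at the second analysis. It is about 2.2- to 2.8-fold in Year 2 and about 1.2-fold for pooled All ETV.

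These sizes rest on a constant event rate, the plan's dropout and placebo seroconversion, and assumed later accrual and other seroconversion. Leaving out seroreversion matters little: at an assumed 40% reversion the second-analysis ratio moves from 1.20 to 1.18. The mismatch itself depends on none of these assumptions. Event counts, subject-level AE and SAE summaries and all efficacy results are untouched. This should be corrected, but it does not threaten the trial's conclusions.

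**What to change.** In SAP 8.10, define person-time for each cohort over the interval in which SAP 7.6 counts its events:

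1. **Through Week 48:** first dose of study therapy to the earliest of 54 weeks, the day before the first open-label ETV dose, and the dose end date of study therapy.
2. **Year 2:** from the same Week 48 cut to the earlier of 102 weeks and the dose end date of study therapy.
3. **All ETV:** first dose date to dose end date of active ETV.

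Apply the earlier of 54 weeks and first open-label dose to every subject. A cut placed at the open-label start for all switchers would fail for Week 48 seroconverters who revert and start open-label ETV later (Protocol 4.1.1), and for subjects kept on blinded drug past 54 weeks (SAP Appendix 1). Their exposure would run beyond the point where event counting stops.

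Use the dose end dates with the existing conventions of SAP 8.9 and 8.2, and add no new data cut-off rule. The last dose date is unsuitable for subjects still on therapy, because it is "derived only for subjects with an end of treatment subject status CRF". Add the 5 days only for subjects who discontinued, and only where those days fall inside the window.

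The cost is a few lines of SAP text and some programming; the dose dates needed are already derived in SAP 8.9.

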## 8.11 Laboratory Test Conversion

ICON changed its chemistry testing platform from the Roche Diagnostics Hitachi Modular system to the Abbott Architect system. Thus, values from the Abbott system are converted to the Roche system for comparability.

Based on regression analyses, laboratory tests which fail to show statistical equivalence between the Roche and the Abbott systems are converted as follows:  $x = (y - c)/m$ , where  $x$  is the Roche value,  $y$  is Abbott value, and  $m$  and  $c$  are respectively the slope and intercept of the regression line (see table below).

Records from the Abbott system are identified with laboratory names containing “ARCHITEC”. Values are converted before applying toxicity grades.

ICON Laboratory Services Dublin Method Comparison, Version 4, 15-Apr-2015							
Method X:	Roche Hitachi Modular 8M, 1284-8			Approved by: [name]		Date:24APR2016	
Method Y:	Abbott Architect a1800881						
Analyte	Slope	Intercept	R Value	X-Method (Modular) Results Range	Y-Method (Architect) Results Range	Units	Statistically Equivalent
Albumin	0.870 (0.786 to 0.954)	1.9 (-1.9 to 5.8)	0.9404	38 to 53	35 to 47	g/L	N
Alkaline Phosphatase	1.011 (0.973 to 1.049)	0.2 (-2.6 to 2.9)	0.9923	40 to 121	36 to 118	U/L	Y
ALT	1.113 (1.023 to 1.203)	-1.1 (-2.7 to 0.5)	0.9655	7 to 41	6 to 45	U/L	N
AST	0.986 (0.931 to 1.041)	-1.1 (-2.3 to 0.2)	0.9822	10 to 57	9 to 57	U/L	Y
Bicarb	0.972 (0.750 to 1.193)	-0.4 (-5.2 to 4.4)	0.7074	17 to 26	16 to 24	mmol/L	N
BUN	0.982 (0.911 to 1.052)	-0.26 (-0.57 to 0.04)	0.9850	3.1 to 9.3	2.7 to 8.9	mmol/L	Y
Calcium	1.002 (0.925 to 1.079)	-0.079 (-0.268 to 0.109)	0.9612	1.57 to 3.20	1.57 to 3.18	mmol/L	Y
Cholesterol	1.081 (1.049 to 1.112)	-0.104 (-0.262 to 0.054)	0.9954	2.85 to 7.48	1.95 to 8.16	mmol/L	N
CK	1.027 (1.013 to 1.040)	-2.9 (-4.9 to -1.0)	0.9990	32 to 428	33 to 443	U/L	N
Chloride	0.949 (0.884 to 1.014)	7.0 (0.5 to 13.6)	0.9610	81 to 111	83 to 112	mmol/L	N
Creatinine (Enzymatic)	0.970 (0.932 to 1.009)	1.25 (-1.82 to 4.33)	0.9914	46.0 to 128.5	45.5 to 123.6	umol/L	Y
Direct Bilirubin	2.750 (2.007 to 3.493)	-2.28 (-3.92 to -0.65)	0.4805	0.0 to 3.0	1.1 to 5.7	umol/L	N
GGT	1.035 (1.018 to 1.052)	0.7 (0.0 to 1.3)	0.9985	6 to 126	7 to 113	U/L	N
Glucose	1.040 (1.006 to 1.074)	-0.176 (-0.465 to 0.113)	0.9943	3.20 to 14.05	3.35 to 14.19	mmol/L	N
HDL	0.824 (0.756 to 0.893)	0.161 (0.068 to 0.255)	0.9610	0.65 to 2.61	0.65 to 2.42	mmol/L	N
Potassium	0.981 (0.908 to 1.054)	-0.02 (-0.38 to 0.31)	0.9686	3.6 to 6.0	3.6 to 5.9	mmol/L	Y
LDH	0.985 (0.898 to 1.072)	-1.3 (-3.0 to 11.5)	0.9558	94 to 210	88 to 198	U/L	Y
LDL	0.953 (0.888 to 1.017)	-0.018 (-0.221 to 0.185)	0.9742	1.08 to 5.36	0.97 to 5.52	mmol/L	Y
Sodium	1.060 (0.991 to 1.129)	-11.8 (-21.5 to -1.8)	0.9652	124 to 164	120 to 161	mmol/L	N
Phosphate	0.987 (0.928 to 1.045)	0.030 (-0.087 to 0.097)	0.9800	0.57 to 1.54	0.58 to 1.59	mmol/L	Y
Total Bilirubin	1.194 (1.109 to 1.278)	0.21 (-0.45 to 0.88)	0.9716	0.0 to 15.0	2.0 to 28.9	umol/L	N
Total Protein	1.026 (0.968 to 1.083)	-6.1 (-10.3 to -1.9)	0.9689	49 to 90	46 to 90	g/L	N
Triglycerides	0.894 (0.859 to 0.929)	0.147 (0.080 to 0.214)	0.9911	0.45 to 3.92	0.61 to 3.26	mmol/L	N
Uric Acid	1.156 (1.076 to 1.237)	-0.51 (-0.90 to -0.13)	0.9728	1.3 to 7.0	1.7 to 7.8	mg/dL	N
Creatinine (Enzymatic) - Urine	0.901 (0.886 to 0.911)	-0.007 (-0.074 to 0.059)	0.9997	1.32 to 29.95	1.73 to 21.71	mmol/L	N
Glucose - Urine	1.033 (1.028 to 1.039)	-0.082 (-0.129 to -0.035)	0.9998	0.02 to 22.65	0.06 to 23.40	mmol/L	N
MicroAlbumin - Urine	1.100 (1.077 to 1.122)	1.3 (0.4 to 2.2)	0.9979	3 to 156	5 to 171	g/L	N

Tests are considered to be statistically equivalent if the following conditions are achieved:	
Slope:	1.00 (within 95% Confidence)
Intercept:	0.0 (within 95% Confidence)
R value:	≥ 0.95

Note: to calculate y, use the formula  $y=mx + c$ , where  $m = \text{slope}$ , and  $c = \text{intercept}$   
For the inverse, use the formula  $(y-c)/m = x$

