#### **7.6.6.1 Laboratory Abnormalities**

For each laboratory test, laboratory abnormalities by toxicity grade (Grade 1 - 4; Grade 3 - 4) on treatment are summarized by treatment regimen and baseline status (all, normal, abnormal, not reported) for the following 3 cohorts:

- Through Week 48 on blinded therapy for treated subjects
- After Week 48 on blinded therapy or on open-label ETV through Week 96 for the Year 2 Safety Cohort
- On ETV treatment for All ETV Safety Cohort

Laboratory tests include:

- Hematology: hemoglobin, platelets, international normalized ratio (INR), white blood cell count (WBC) and neutrophils + bands (absolute)
- Liver function tests: alanine aminotransferase (ALT), aspartate aminotransferase (AST), total bilirubin and albumin
- Pancreatic enzymes: lipase (colorimetric or turbidimetric assay)
- Renal function tests: creatinine and BUN/urea (BUN or urea)
- Electrolytes (low and high): chloride, potassium and sodium.

Toxicity grades are based on DAIDS, unless specified otherwise (see Protocol Appendix 2). BUN/urea and chloride are graded with modified WHO criteria.

Treatment emergent laboratory abnormalities by toxicity grade (increased to Grades 1, 2, 3 and 4) are also summarized analogously by treatment regimen and baseline status for the 3 cohorts. On-treatment emergent abnormalities are those with a higher toxicity grade than the baseline toxicity grade (including not reported baseline).

In addition, the following select laboratory elevations and abnormalities on treatment are summarized by treatment regimen for the 3 cohorts:

- Any Grade 3 - 4 laboratory abnormality (see previous list of tests)
- Liver function elevations  $> 2$  and  $> 3$  x baseline (ALT, AST, total bilirubin)
- Liver function elevations  $> 2$  x baseline and Grade 4 (ALT, AST and total bilirubin; includes ALT flares, defined as ALT  $> 2$  x baseline and  $> 10$  x ULN)
- Simultaneous ALT and total bilirubin elevations (ALT  $> 2$  x baseline, total bilirubin  $> 2$  x baseline and  $> 2$  x ULN; ie, those occurring on the same collection day).

- Albumin < 2.5 g/dL
- Lipase elevations > 3 x baseline
- Confirmed creatinine elevations  $\geq 0.3$  and  $\geq 0.5$  mg/mL from baseline (2 sequential measurement or last measurement meeting the elevation criteria)
- Glucose categories (< 50,  $\geq 200$  mg/dL) regardless of fasting status.

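### SAP 8.11 reads non-significance as equivalence, so AST, BUN and potassium stay unconverted although the SAP's own fitted lines put Abbott below Roche throughout

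*SAP*

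**What the plan says.** SAP 8.11 says that Abbott values are put on the Roche scale so that results are comparable, and that conversion precedes toxicity grading. Conversion is selective: "laboratory tests which fail to show statistical equivalence between the Roche and the Abbott systems are converted as follows", with x = (y − c)/m, where x is the Roche value, y the Abbott value, m the slope and c the intercept.

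The selection rule stands below the method-comparison table: "Tests are considered to be statistically equivalent if the following conditions are achieved". The slope condition is "1.00 (within 95% Confidence"), the intercept condition is "0.0 (within 95% Confidence"), and R must be at least 0.95. No allowable difference is given for any test.

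AST (slope "0.986 (0.931 to 1.041")), BUN (slope "0.982 (0.911 to 1.052")) and potassium are all marked equivalent. All three are graded in SAP 7.6.6.1, where BUN appears under "Renal function tests: creatinine and BUN/urea (BUN or urea"). AST is also counted at more than 2 and more than 3 times baseline, and in follow-up relative to end-of-dosing (EOD) and reference values.

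**The concern.** A confidence interval that contains the null value does not show that a difference is negligible. Without a margin, a wide interval helps a test to pass and a narrow one makes it fail. Slope and intercept are also judged one at a time, although their estimation errors are strongly negatively correlated, so a consistent offset shared between them can pass both checks. R describes how tightly the points follow a line, not whether that line is the line of identity.

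If a real platform shift is left in, a subject with a Roche reference value and a later Abbott value shows a change that is partly instrumental. Here it would understate rises in AST and BUN and push potassium towards the low grades.

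**Working it through.** **1. Reproduce the plan's flags.** Applying the three conditions to all 27 rows of the SAP 8.11 table reproduces 27 of 27 flags, so the reading of the rule is secure. Dropping the R condition changes only bicarbonate, so R decides nothing for the three tests at issue.

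**2. Shift implied by the SAP's own lines.** Abbott − Roche = (m − 1)x + c, over the printed Roche ranges.

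| Test | m | c | Low end | Mid-level | High end |
|---|---|---|---|---|---|
| AST, U/L | 0.986 | −1.1 | at 10: −1.24 (−12.4%) | at 20: −1.38 (−6.9%) | at 57: −1.90 (−3.3%) |
| BUN, mmol/L | 0.982 | −0.26 | at 3.1: −0.316 (−10.2%) | at 4.0: −0.332 (−8.3%) | at 9.3: −0.427 (−4.6%) |
| Potassium, mmol/L | 0.981 | −0.02 | at 3.6: −0.088 | at 4.0: −0.096 | at 6.0: −0.134 |

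Example: AST at 20 is 0.986 × 20 − 1.1 = 18.62, so the shift is −1.38. All three lines lie below identity across the tested range.

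**3. The flags need not follow the size of the bias.** Glucose (1.040, −0.176) is converted, yet at 5 mmol/L it gives 5.024, a shift of +0.5%. CK (1.027, −2.9) fails because its intervals are narrow, yet at 100 U/L it gives 99.8, a shift of −0.2%.

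**4. Is the shift more than noise?** Assume ordinary least squares. The half-width of the 95% CI for the fitted line at the sample mean is then the slope half-width times the SD of x (with divisor n). The SD is not printed. Taking it as one third of the Roche range, the widest of the values tried (range/3 to range/6):

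- AST: 0.055 × 47/3 = 0.86; the smallest shift in the range is 1.24.
- BUN: 0.0705 × 6.2/3 = 0.146; the smallest shift is 0.316.
- Potassium: 0.073 × 2.4/3 = 0.058; the smallest shift is 0.088.

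In each case the shift exceeds the half-width wherever in the tested range the mean lies. This step needs neither n nor the intercept CI.

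Using the intercept CI as well places the mean. The ratio of intercept to slope half-width is the root mean square of x, and R with the slope CI implies n of about 50, 27 and 50. With SD = range/3 the mean shifts are:

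- AST: −1.33 (−2.19 to −0.48) U/L
- BUN: −0.33 (−0.47 to −0.19) mmol/L
- Potassium: −0.109 (−0.166 to −0.051) mmol/L

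Smaller SDs give narrower intervals.

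**5. Consequence for an AST multiple.** With a Roche baseline of 20 U/L, an Abbott reading of 40 corresponds to (40 + 1.1)/0.986 = 41.7 on the Roche scale, and 41.7/20 = 2.08. The threshold of 2 therefore acts as about 2.08.

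**6. Consequence for potassium grades.** Roche 3.5 maps to 0.981 × 3.5 − 0.02 = 3.41 on Abbott. Grade 1 low in Protocol Appendix 2 is 3.0 to 3.4. This lies just below the fitted range, so it is an extrapolation.

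**7. High AST.** Extrapolated, the shift is −3.9 U/L (−2.0%) at 200 U/L and −6.7 (−1.7%) at 400.

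**The case against.** The strongest reply is that little depends on these three tests. The tables of laboratory values over time (SAP 7.6.6.2) include none of them. ALT, total bilirubin and albumin are already converted, and with them the ALT flares, the simultaneous ALT and bilirubin elevations and the ALT efficacy endpoint. SAP 7.6.6.1 resets a Grade 1 result to normal when the original value lies within normal limits. The modified WHO cut-offs used to grade BUN are not printed, so no BUN event effect can be calculated. All of this stands and limits the size of the point. The reset is only partial protection, though: it can remove a spurious low-potassium Grade 1, but it cannot restore an AST or BUN grade that was missed.

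The precision can also be challenged. The SAP gives neither n nor the regression type, and the half-width ratio gives impossible values in other rows. For LDH it is 7.25/0.087 = 83, below the printed minimum of 94; for phosphate it is 0.092/0.0585 = 1.57, above the maximum of 1.54. Some printed limits are therefore unreliable. The first check in step 4 avoids that ratio, but it still assumes least squares and an SD of at most one third of the range.

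A reader might infer more than the documents support:

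- *AST is about 7% low throughout.* That holds near 20 U/L; the shift is −4.2% at 40 and −3.3% at 57.
- *The rule always favours the larger bias.* ALT is converted at +5.8% at 20 U/L while AST at −6.9% is not, but at 40 U/L ALT is +8.6% and AST −4.2%.
- *The rule has a known miss rate.* Any such figure depends on an assumed n and distribution, so none is claimed.
- *Serious liver toxicity or the randomised comparison is distorted.* Grade 3–4 AST barely moves, the summaries are descriptive, and nothing suggests that the platform change was specific to one arm.
- *The harm falls in long-term follow-up.* The SAP gives no switch date; the dates on the table belong to the comparison report.

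**Conclusion.** The point holds, at moderate weight. The rule in SAP 8.11 cannot establish equivalence, and it leaves three graded tests short of the comparability that the section sets as its aim. The point estimates come straight from the SAP's lines. That the mean shifts exclude zero rests on assumed ordinary least squares and on the spread of x in step 4.

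What is exposed is narrow: toxicity grades of AST, BUN and potassium, and AST multiples where the reference value is Roche and the later value Abbott. How many subjects that covers cannot be determined from the documents. The primary endpoint is not touched, because HBV DNA and serology are not in this table.

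**What to change.** In SAP 8.11, stop using the equivalence verdict to exclude AST, BUN and potassium. Apply x = (y − c)/m to them on the same terms as the tests already converted.

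Do not restrict conversion to the fitted range. The SAP sets no such limit for ALT, whose Roche range was only 7 to 41 U/L. A limit would leave low-potassium grades (3.4 and below, against a fitted minimum of 3.6) unconverted. It would do the same for AST doublings from baselines above about 28 U/L (57/2 = 28.5). Flag values outside the fitted range as extrapolated instead.

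Show the affected SAP 7.6.6.1 tables with and without this conversion. Creatinine need not be added: its line gives −0.3% at 46 and −2.0% at 128.5 µmol/L.

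The cost is a change of SAP wording, a few lines of code and a few extra tables, since the coefficients are already printed. No new data are needed. The downside is that three more tests carry regression error in their converted values.
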